### **7.5.2. Inflammatory Markers**

Baseline and postbaseline levels of inflammatory markers will be summarized for the safety population. These markers include serum ferritin, CRP, D-dimer, procalcitonin, and IL-6. Changes and percentage changes in each marker will be summarized at Day 15 and Day 29.

### **7.5.3. SARS-CoV2 Virologic and Serologic Parameters**

Baseline and postbaseline levels of viral load and anti-SARS-CoV-2 antibodies will be summarized for the safety population at Study Days 1, 15, and 29. The proportion of participants negative for SARS-CoV2 will be summarized at Day 15 and Day 29.

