	• Participants who are on long-term use of antirejection or immunomodulatory drugs.	
	Pregnant or nursing (lactating) women.	
Study treatment	Ruxolitinib 5 mg BID, ruxolitinib 15 mg BID, or matching-image placebo (placebo randomized 1:1 to match ruxolitinib 5 mg or 15 mg) for 14 days with possible extension of treatment to 28 days	
Treatment of interest	Ruxolitinib 5 mg tablets	
Principal coordinating investigator		
Efficacy assessments	Overall survival through Study Day 29	
	• In-hospital outcomes	
	Clinical status using a 9-point ordinal scale	
	• Vital signs, oxygenation and ventilator parameters	
	SOFA score	
Key safety assessments	Adverse event monitoring through safety follow-up period	
	Laboratory markers	
	SARS-CoV-2 viral load	
Other assessments	Inflammatory markers including ferritin, CRP, D-dimer, procalcitonin, IL-6 at sites where feasible	

Data analysis	Individual comparisons between placebo and ruxolitinib treatment groups will be performed in a pairwise fashion (placebo vs 5 mg BID and placebo vs 15 mg BID). The primary endpoint of the Day 28 mortality rate will be analyzed using the ITT population using a logistic regression model including treatment group, ARDS severity mild/moderate (PaO ₂ /FiO ₂ > 100 to \leq 300 mmHg) vs severe (PaO ₂ /FiO ₂ \leq 100 mmHg), and gender as fixed effects and investigational site as a random effect. The statistical test will test the null hypothesis that the odds-ratio between ruxolitinib and placebo treatment is 1 with a 1-sided test. Overall familywise Type I error control of 2.5% (1-sided) will be accomplished using a Dunnett's procedure, where the nominal alpha level for the individual comparisons will be adjusted to 0.01436968. An interim analysis for efficacy is intended when the first 40% of the planned randomized participants have died or have reached their Day 29 assessment, and additional futility analyses for the primary endpoint based on a Cox regression model are planned weekly for the study.		

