Exploratory			
To evaluate the efficacy of ruxolitinib + SoC therapy compared with placebo + SoC therapy in proportion of participants requiring IL-6, IL-1, GM-CSF, or JAK-directed therapies.	Proportion of participants requiring treatments with IL-6, IL-6R, IL-1RA, IL-1β, GM-CSF, BTK, or JAK-directed therapies by Day 15 and by Day 29		
To evaluate ruxolitinib + SoC therapy compared with placebo + SoC therapy on change in inflammatory markers (when available).	 Change from baseline to Day 15 and to Day 29 in the following clinical chemistry measurements: Serum ferritin CRP D-dimer Procalcitonin IL-6 		
To evaluate ruxolitinib + SoC therapy compared with placebo + SoC therapy on change in COVID-19 virologic and serologic parameters.	Change from baseline to Day 15 and to Day 29 in viral load and anti-SARS-CoV2-antibody titer.		

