9.4.2. Presence SARS-CoV-2 Virus/Viral Load/Antibody Testing

For the screening inclusion criterion, SARS-CoV-2 virus is to be measured by PCR or by other locally approved diagnostic methodology ≤ 3 weeks of randomization. Documentation of the method used should be available in the source notes. Viral load and antibody testing may be performed by any approved method and is only required if local capabilities allow; a consistent method and specimen source should be used at all timepoints.

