12.4.3. Exploratory Efficacy Analyses

Change from baseline to Day 15 and Day 29 in serum ferritin, C-reactive protein (CRP), D-dimer, IL-6, and viral load will be summarized by treatment arm. Additional details will be provided in the Statistical Analysis Plan.

Exploratory endpoints will be summarized descriptively using ITT population.

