**Table 1: Objectives and Endpoints (Continued)**

Objectives	Endpoints
To evaluate the efficacy of ruxolitinib 5 mg BID + SoC therapy and ruxolitinib 15 mg BID + SoC therapy compared with placebo + SoC therapy on change from baseline SOFA score in participants with COVID-19–associated ARDS who require mechanical ventilation.	Change from baseline to Day 3, 5, 8, 11, 15, and 29 in SOFA score.
To evaluate the safety of ruxolitinib 5 mg BID + SoC therapy and ruxolitinib 15 mg BID + SoC therapy compared with placebo + SoC therapy in the treatment of participants with COVID-19–associated ARDS who require mechanical ventilation.	Number and proportion of participants with treatment-related side effects (as assessed by CTCAE v5.0) and SAEs; includes clinically significant changes in laboratory measures and vital signs.
Exploratory	
To evaluate the efficacy of ruxolitinib + SoC therapy compared with placebo + SoC therapy in proportion of participants requiring IL-6, IL-1, GM-CSF, or JAK-directed therapies.	Proportion of participants requiring treatments with IL-6, IL-6RA, IL-1RA, IL-1 beta, GM-CSF, BTK, or JAK directed therapies by Day 15 and by Day 29.
To evaluate ruxolitinib + SoC therapy compared with placebo + SoC therapy on change in inflammatory markers (when available).	Change from baseline to Day 15 and to Day 29 in the following clinical chemistry measurements: 
 
• Serum ferritin
 
• CRP
 
• D-dimer
 
• Procalcitonin
 
• IL-6
 

To evaluate ruxolitinib + SoC therapy compared with placebo + SoC therapy on change in COVID-19 virologic and serologic parameters.	Change from baseline to Day 15 and Day 29 in viral load and anti–SARS-CoV-2-antibody titer.

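### SAP 7.5.3 drops the stated virology endpoint, change from baseline to Days 15 and 29, without listing it as a change, leaving levels from mixed local assays and the proportion negative

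*SAP*

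**What the plan says.** **Endpoint.** Protocol Table 4 lists, among the exploratory endpoints, "Change from baseline to Day 15 and to Day 29 in viral load and anti-SARS-CoV2-antibody titer". SAP Table 1 keeps it: "Change from baseline to Day 15 and Day 29 in viral load", again with antibody titer.

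**Protocol analysis.** Section 12.4.3 applies change from baseline to Days 15 and 29 to several markers, ending with "IL-6, and viral load will be summarized by treatment arm". It leaves further detail to the SAP. Antibody titer is not in that list.

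**SAP analysis.** Section 7.5.3 states: "Baseline and postbaseline levels of viral load and anti-SARS-CoV-2 antibodies will be summarized" for the safety population at Days 1, 15 and 29. The next sentence adds the proportion of participants negative at Days 15 and 29. Neither sentence mentions change. Section 7.5.2, just before it, does plan changes and percentage changes for the inflammatory markers.

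**Measurement.** Protocol 9.4.2 says "Viral load and antibody testing may be performed by any approved method and is only required if local capabilities allow". It also asks for the same method and specimen source at all timepoints.

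**Status.** Protocol Table 2 names "SARS-CoV-2 viral load" among the key safety assessments, and 9.4.2 sits under Safety. Both objectives tables class the endpoint as exploratory, and SAP Section 9 (safety) has no viral-load analysis.

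**The concern.** The SAP names one quantity as the endpoint and plans summaries of others. The omitted quantity is also the one the collection rule supports. A constant method and specimen source make a participant's own change interpretable, but they do not put participants at different sites on a common scale.

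Ruxolitinib suppresses immune signalling. Protocol 5.6 names infection as a risk and reports viral-load increases in chronic hepatitis B. A reader of the study report would therefore want to know whether SARS-CoV-2 cleared more slowly on active drug. With the planned displays that reader has levels mixed over assays, and a proportion negative whose denominator is not stated. At Day 29 many participants may have died, and others may never have been tested.

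**Working it through.** **1. Texts side by side**

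| Place | Change from baseline | Levels | Proportion negative |
|---|---|---|---|
| Protocol Table 4 (endpoint) | yes | – | – |
| SAP Table 1 (endpoint) | yes | – | – |
| Protocol 12.4.3 (viral load) | yes, by arm | – | – |
| SAP 7.5.3 | no | yes | yes |
| SAP Appendix A, Tables 2.3.3.1 and 2.3.3.2 (titles) | not named | visits named | – |
| SAP 11.1 (changes to protocol-defined analyses) | omission not listed | – | – |

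The SAP also gives no rule for assay, unit, measurement scale, detection limit, untested participants or deaths for this endpoint.

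**2. How much the choice of summary could matter**

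The documents give no viral-load figure to reproduce, and SAP 7.5.3 plans no test. Power at two-sided 5% is used only as a measure of how visible a difference would be.

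From the SAP: 211 participants at 2:2:1 gives 211/5 = 42.2, so about 42 placebo and 84 per ruxolitinib arm.

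Assumed: baseline mean 6 log10 with SD 1.3; change −3 with SD 1.5 on placebo; ruxolitinib slower by 1 log10; three equally common assays offset by −0.7, 0 and +0.7 log10; everyone tested at Day 15.

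Both SEs use √(1/42 + 1/84) = 0.189.

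- *Within-participant log10 change.* The assay offset cancels. SE = 1.5 × 0.189 = 0.2835. Power = Φ(1/0.2835 − 1.96) = Φ(1.57) ≈ 94%.
- *Day 15 level.* The offset variance is 0.49 × 2/3 = 0.327. SD = √(1.69 + 2.25 + 0.327) = 2.066 and SE = 2.066 × 0.189 = 0.390. A comparison of log10 means gives Φ(1/0.390 − 1.96) = Φ(0.60) ≈ 73%. A rank comparison, which does not depend on scale, gives about 70% by simulation.
- *Proportion negative, assumed detection limit 2.5 log10.* Placebo: Φ((2.5 − 3)/2.066) = 0.404. Ruxolitinib: Φ((2.5 − 4)/2.066) = 0.234. Difference 0.170. Pooled proportion 0.291, so the null SE is √(0.291 × 0.709/28) = 0.086. The alternative SE is √(0.404 × 0.596/42 + 0.234 × 0.766/84) = 0.089. Power = Φ((0.170 − 1.96 × 0.086)/0.089) ≈ 50%.

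Simulation (4000 trials per scenario), with the same detection limit of 2.5:

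| Scenario | log10 change | Rank of levels | Proportion negative |
|---|---|---|---|
| 42 vs 84, 1 log10 | 94% | 70% | about 50% |
| 42 vs 84, 0.7 log10 | 68% | 41% | 30% |
| 20 vs 50 tested, 1 log10 | 69% | 42% | 31% |

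**3. Where the advantage shrinks**

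- *Detection limit.* The first two columns treat every result as quantified. If values below 2.5 are set to 2.5 in the first scenario, simulation gives about 81% for log10 change and 66% for ranks.
- *Correlation.* With biological SD σ at each visit, correlation ρ and assay SD s, a level has SD √(σ² + s²) and a change has SD √(2σ²(1 − ρ)). For σ = 2 and s = 1, that is 2.24 against 1.55 at ρ = 0.7, 2.24 against 2.00 at ρ = 0.5, and 2.24 against 2.37 at ρ = 0.3. The inputs in step 2 imply ρ = 1.3/√(1.69 + 2.25) = 0.65. With weak correlation and modest assay offsets, change is no better than levels.

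**The case against.** A reader might infer that viral load is shown only as pooled raw levels, so that delayed clearance on an immunosuppressant could not be detected. The documents do not support that.

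- The proportion negative at Days 15 and 29 is a direct, if coarse, measure of clearance and needs no common unit.
- SAP 5.1 requires the median, minimum and maximum, so a few very high values need not dominate the display.
- SAP 5.2 keeps treatment groups apart. Mixing across assays is inferred from the SAP's silence, and arms are not pooled.
- Randomisation is blocked and stratified by site, so the local assay mix should be roughly balanced between arms.

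It is also tempting to contrast log10 change with mean change on the raw scale, which has only about 1% power under the same inputs. The SAP plans no such analysis, so that contrast says nothing about what would be lost.

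Further points against: the endpoint is exploratory and testing depends on local capability; Listings 2.6.12 and 2.6.13 show individual virology and serology; and the table shells are in a separate document, so a change column cannot be excluded.

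All of this stands and limits the point. It does not remove the mismatch between the endpoint and SAP 7.5.3. Site stratification guards against bias from assay mix, but not against between-assay noise, and it does not ensure balance among those tested. The proportion negative has no stated denominator.

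**Conclusion.** The point holds as an omission. SAP 7.5.3 does not plan the change from baseline that both objectives tables define, and that Protocol 12.4.3 promises by arm for viral load. SAP 11.1 does not record the departure.

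The consequence is reduced visibility of a clearance difference. Under the assumed inputs (1 log10 slowing, 42 vs 84), that is about 94% for log10 change against 70% for ranked levels and 50% for the proportion negative. The gap narrows with a detection limit and can disappear if baseline and follow-up are weakly correlated. None of the viral-load inputs is a document figure. Priority is low: the endpoint is exploratory and descriptive, and no primary or secondary conclusion depends on it.

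**What to change.** In SAP 7.5.3 and Tables 2.3.3.1 and 2.3.3.2:

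1. Add within-participant log10 change in viral load, and log ratio for antibody titer, from baseline to Days 15 and 29, by arm with 95% CI. State how results below the detection limit enter.
2. Show the number tested per arm and visit.
3. Keep the proportion negative and state its denominator, including how deaths and untested participants are counted.
4. Restrict to pairs with the same method and specimen source, or split by result type, only where the database records these. Protocol 9.4.2 asks for documentation of the method in connection with the screening test and does not clearly extend this to later samples or to specimen source.

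If leaving out change was intended, list it in SAP 11.1 with the reason.

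The cost is SAP wording and two reprogrammed tables, with no new visit or sample. The downside is that participants without a comparable baseline and follow-up pair drop out of the change summary.

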## **8. PHARMACODYNAMICS**

See Section [7.5](#) for details regarding pharmacodynamic endpoints.

## **9. SAFETY AND TOLERABILITY**

[Appendix A](#) provides a list of data displays. Sample data displays are included in a separate document.

### **9.1. General Considerations**

Summary tables may be replaced with listings when appropriate. For instance, an AE frequency table may be replaced with a listing if it only contains a few unique PTs reported on relatively few participants.

### **9.2. Adverse Events**

#### **9.2.1. Adverse Event Definitions**

A TEAE is any AE either reported for the first time or worsening of a pre-existing event after the first dose of study drug until 31 days after the last dose of study drug. Analysis of AEs (as discussed below) will be limited to TEAEs, but data listings will include all AEs regardless of their timing in relation to study drug administration. For purposes of analysis, all AEs will be considered TEAEs unless the AE can unequivocally be defined as not treatment-emergent.

Adverse events will be tabulated by MedDRA PT and SOC. Severity of AEs will be graded using the NCI CTCAE v5. The CTCAE reporting guidelines and grading details are available on the Cancer Therapy Evaluation Program website.

The subset of AEs considered by the investigator to be related to study drug will be considered to be treatment-related AEs. If the investigator does not specify the relationship of the AE to study drug, the AE will be considered to be treatment-related. The incidence of AEs and treatment-related AEs will be tabulated. In addition, serious TEAEs will also be tabulated.

### 9.2.2. Adverse Event Summaries

An overall summary of AEs by treatment group will include the following:

- Number (%) of participants who had any TEAEs
- Number (%) of participants who had any serious TEAEs
- Number (%) of participants who had any Grade 3 or higher TEAEs
- Number (%) of participants who had any TEAEs related to ruxolitinib/placebo
- Number (%) of participants who temporarily interrupted ruxolitinib/placebo because of TEAEs
- Number (%) of participants who permanently discontinued ruxolitinib/placebo because of TEAEs
- Number (%) of participants who had ruxolitinib/placebo dose reductions because of TEAEs
- Number (%) of participants who had any fatal TEAEs

The following summaries will be produced:

- Summary of TEAEs by MedDRA SOC and PT
- Summary of TEAEs by MedDRA PT in decreasing order of frequency
- Summary of TEAEs by MedDRA SOC, PT, and maximum severity category
- Summary of Grade 3 or higher TEAEs by MedDRA SOC and PT
- Summary of Grade 3 or higher TEAEs by MedDRA PT in decreasing order of frequency
- Summary of serious TEAEs by MedDRA SOC and PT
- Summary of serious TEAEs by MedDRA PT in decreasing order of frequency
- Summary of ruxolitinib/placebo treatment-related TEAEs by MedDRA SOC and PT
- Summary of ruxolitinib/placebo treatment-related TEAEs by MedDRA PT in decreasing order of frequency
- Summary of ruxolitinib/placebo treatment-related TEAEs by MedDRA SOC, PT, and CTCAE grade category
- Summary of Grade 3 or higher ruxolitinib/placebo treatment-related TEAEs by MedDRA SOC and PT
- Summary of ruxolitinib/placebo treatment-related serious TEAEs by MedDRA SOC and PT
- Summary of TEAEs with a fatal outcome by MedDRA SOC and PT
- Summary of TEAEs leading to ruxolitinib/placebo dose reduction by MedDRA SOC and PT

- Summary of TEAEs leading to ruxolitinib/placebo dose interruption by MedDRA SOC and PT
- Summary of TEAEs leading to discontinuation of ruxolitinib/placebo by MedDRA SOC and PT
- Summary of TEAEs requiring concomitant medications by MedDRA SOC and PT

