7.1.2. Treatment Duration

The planned initial duration of treatment is 14 days. Treatment may be extended to an additional 14 days (ie, Days 15-28) at the discretion of the investigator, if the benefits of treatment outweigh the risks, and with approval from the sponsor medical monitor. Approval must be requested \geq 24 hours before initiation of dosing on Day 15. Participants may be discontinued from treatment earlier due to unacceptable toxicity, progression/worsening of COVID-19 ARDS, or resolution/improvement of COVID-19 symptoms and/or at the discretion of the investigator or the participant. Treatment will not be provided upon completion of the study.

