12.4.2. Safety Analyses

Safety analyses will be conducted for the safety population. Adverse events will be coded by the MedDRA dictionary, and TEAEs (ie, AEs reported for the first time or worsening of a pre-existing event after first dose of study drug/treatment) will be tabulated by preferred term and system organ class for all events, related events, SAEs, and events of Grade 3 or higher. Quantitative safety variables and their changes from baseline (eg, laboratory, vital signs) will be summarized with descriptive statistics.

The clinical laboratory data will be analyzed using summary statistics; no formal treatment group comparisons are planned. In addition, distributions of key laboratory parameters (eg, IL-6, ferritin, platelets) may be plotted over time; these values will also be classified into CTCAE toxicity grades, and tabulated. Descriptive statistics and mean change from baseline will be determined for vital signs at each assessment time.

Measures of exposure (eg, days of exposure, duration of treatment, and average daily dose) of study drug and/or reference therapy will be summarized by means of summary statistics.

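### Adverse events are summarized only as crude percentages over a window set by treatment duration and cut short by death, so a difference in mortality or duration can shift the percentages with equal event rates; supplementary fixed-window and rate displays would show it

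*SAP*

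**What the plan says.** The overall summary in SAP 9.2.2 consists of rows of the type "Number (%) of participants who had any TEAEs". The remaining items there, and Appendix A tables 3.2.1 to 3.2.21, are summaries by system organ class, preferred term, severity, relationship and action taken. SAP 5.1 defines a categorical summary as number and percentage. Protocol 12.4.2 likewise says only that events "will be tabulated by preferred term and system organ class for all events, related events, SAEs, and events of Grade 3 or higher".

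Under SAP 9.2.1 an event is treatment-emergent if it is new, or worsens, "after the first dose of study drug until 31 days after the last dose of study drug". Protocol 7.1.2 lets the last dose move:
- Dosing is set at two weeks to begin with.
- It can go on longer: "Treatment may be extended to an additional 14 days (ie, Days 15-28) at the discretion of the investigator", with medical monitor approval.
- It can also stop sooner: "Participants may be discontinued from treatment earlier due to unacceptable toxicity, progression/worsening of COVID-19 ARDS, or resolution/improvement of COVID-19 symptoms".

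SAP 6.4 summarizes treatment duration and average daily dose, but separately; neither is a denominator for any adverse event table. Neither document plans an exposure-adjusted rate, a time-to-first-event or cumulative incidence analysis, or a common adverse event window. For efficacy the SAP does deal with death explicitly: zero event-free days (7.4.1), ordinal category 8 (7.4.2) and the worst SOFA component score (7.4.3.2). Adverse events have no counterpart.

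**The concern.** Safety of each dose against placebo is a stated secondary objective and no formal adverse event test is planned, so the percentages are the comparison. A participant whose last dose is on Day 3, 14 or 28 is observed until Day 34, 45 or 59 if alive (last dose day + 31). A participant who dies is observed only until death. Under Protocol 11.1 and 11.2, disease progression and death from it are not adverse events, so such a death shortens observation without adding an event.

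An arm with lower mortality or longer treatment therefore has more time in which to record events, and its percentages can rise with no change in the daily rate. An arm with higher mortality can look better than its event rate warrants. The planned tables cannot separate a different event rate from different time at risk.

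**Working it through.** **Mortality inputs.** The documents give no adverse event frequencies. The only stated calculation using the mortality rates is the power figure in SAP 3.3: 60% versus 40%, 100 versus 200 participants, 1-sided alpha 0.01436968, about 83%.
- Pooled rate = (60 + 80)/300 = 0.467. Null SE = √(0.467 × 0.533 × (1/100 + 1/200)) = 0.0611. Alternative SE = √(0.24/100 + 0.24/200) = 0.0600. Critical z = 2.187.
- Uncorrected: (0.20 − 2.187 × 0.0611)/0.0600 = 1.106, power 86.6%, in line with the simulated 0.868 to 0.872 in SAP Table 2.
- With continuity correction 0.0075: 0.981, power 83.7%.

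The stated figure is reproduced and not in dispute. Only its mortality rates are used below.

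**Model (assumptions).** Event hazard λ is constant and the same in both arms, and independent of death. The death hazard is constant to 28 days, with no deaths after that. Observation ends at death or at the end of the window.
- μ = −ln(1 − m)/28: 0.03272 per day at 60%, 0.01824 at 40%.
- Assumed 28-day event risk absent death 30%: λ = −ln(0.7)/28 = 0.01274 per day.

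**28-day window.** Crude % = λ/(λ + μ) × (1 − e^(−28(λ+μ))), where the exponential equals 0.7 × (1 − m).
- Placebo: 0.2802 × (1 − 0.28) = 20.2%.
- Ruxolitinib: 0.4112 × (1 − 0.42) = 23.8%.

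**45-day window (last dose Day 14).** Add the next 17 days for event-free survivors; 1 − e^(−17λ) = 0.1947.
- Placebo: 20.17 + 28 × 0.1947 = 25.6%.
- Ruxolitinib: 23.85 + 42 × 0.1947 = 32.0%.
- Mean days alive in the window, (1 − e^(−28μ))/μ + 17(1 − m): 18.3 + 6.8 = 25.1 versus 21.9 + 10.2 = 32.1, or 28% more.
- Rate, events divided by days to first event, death or end of window: 1.27 versus 1.27 per 100 participant-days. The rates are equal, as the model requires.

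**How the gap varies** (45 days, same event unless stated).

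| Scenario | Placebo | Ruxolitinib |
|---|---|---|
| Mortality 60% vs 55% | 25.6% | 27.3% (+1.7) |
| Mortality 60% vs 50% | 25.6% | 28.9% (+3.3) |
| Mortality 60% vs 60%, same window | 25.6% | 25.6% (0) |
| Mortality 60% vs 70% (pure assumption) | 25.6% | 22.1% (−3.5) |
| Deaths continue after Day 28, 60% vs 40% | 24.4% | 30.9% (+6.5) |

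Window length alone, at 60% mortality, moves the figure from 25.6% (45 days) to 29.3% (59 days).

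**Early events.** Confine a 30% risk to the first k days: λ = −ln(0.7)/k, crude % = λ/(λ + μ) × (1 − e^(−k(λ+μ))), mortality 60% versus 40%. For the rate, divide by mean days to first event, death or end of window.

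| Hazard confined to | Crude % | Crude ratio | Rate ratio, 45 days | Rate ratio, 28 days |
|---|---|---|---|---|
| 7 days | 27.0 vs 28.3 | 1.05 | 0.83 | 0.88 |
| 14 days | 24.4 vs 26.7 | 1.09 | 0.87 | 0.93 |

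The true hazards are equal throughout. The crude percentage drifts slightly against the arm that survives longer. The rate errs further the other way, because that arm adds person-time in which no events can occur.

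**The case against.** **The crude percentage is not an error.** It is a valid absolute risk in the presence of death, and number and proportion is the declared safety endpoint. This stands: other measures should sit beside it, not replace it.

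**Rates can be worse.** With 14 days of planned dosing and a 31-day tail off drug, early-concentrated events are plausible, and the second table shows the rate then misleads more than the percentage. This stands and limits the remedy.

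**The size is uncertain.** 60% versus 40% is the powering alternative, not a forecast. With 211 randomized (about 42 placebo and 84 per dose under 2:2:1), the standard error of 25.6% versus 32.0% is √(0.256 × 0.744/42 + 0.320 × 0.680/84) = 8.4 points, more than the 6.4-point shift. The any-TEAE row may be least affected if nearly everyone has an early event. All true, but the shift is systematic where sampling error is not, and later events of intermediate frequency are more exposed.

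**Stronger readings to resist.**
- A reader might give every ruxolitinib participant the extended window and no placebo participant, and infer a much larger gap. Extension is decided under blinding (Protocol 7.4) with medical monitor approval, so all-versus-none is not credible.
- A reader might infer that infection or cytopenia harm would be hidden. Hematology is summarized by scheduled day with CTCAE shift tables (SAP 9.3.2), mortality is the primary endpoint, fatal events are tabulated, and a DMC monitors deaths and serious events (Protocol 5.3).
- A reader might infer that every shell is a bare percentage. SAP 9.2.2 writes number and percentage only for the overall summary, and the shells are in a separate document. What can be said is that the SAP names no other measure.

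**Conclusion.** The point holds as a gap in the safety displays, not as an error in the declared endpoint. The adverse event window depends on post-randomization treatment duration and is truncated by death, and no planned display takes this into account. A mortality or duration difference can therefore move the percentages with equal event rates.

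At the design mortality rates, for an event with 30% 28-day risk, the shift is about 6.4 points over 45 days and 3.7 points over 28 days. It halves at 60% versus 50% mortality, is about 1 point if the hazard lasts only 7 days, and vanishes without a mortality or duration difference. These sizes rest on assumed event frequency, constant equal hazards and independence of events from death; correlation between events and death would change them.

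The documents do not support saying that the crude figures are invalid, that ruxolitinib will look less safe, or that rates should carry the safety conclusion. Priority is a supplementary analysis; the primary mortality conclusion is unaffected.

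**What to change.** In SAP 9.2.2 keep the crude number and percentage as the declared endpoint. For any, serious, Grade 3 or higher and treatment-related TEAEs, and for the main system organ class and preferred term tables, add as supplementary displays:

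- (a) the same summary in a fixed Day 1-29 window, as cumulative incidence with death as a competing event;
- (b) the exposure-adjusted incidence rate in that window: participants with the event divided by participant-days to first event, death or end of window;
- (c) mean time at risk by arm.

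State that the measures are read together. Display (a) removes the dependence on the extension decision but not on death (20.2% versus 23.8% above). Display (b) allows for time at risk but is reliable only if the hazard is roughly constant. The between-arm safety statement should not rest on the rates alone.

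The cost is SAP wording and longer tables, plus a constant-hazard caveat on the rates. Dose, event onset and death dates are already collected. Any dosed participant's TEAE window runs to at least Day 32 if alive (1 + 31), so Day 1-29 lies inside it and no trial procedure changes.
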